5.4 Blinding Procedures

We describe this study as a 3-arm randomized controlled trial in which two treatment arms are double blinded and the third arm consists of a no-treatment group that is partially unblinded to only the unblinded monitor (who will be unblinded to treatment arm but blinded to treatment identity). Other than this person, all the remaining personnel conducting the study, collecting study endpoints, and analyzing data, including the PI, will be blind to the allocation of participants to study arm, response prediction, and treatment. All pills will be identically encapsulated to ensure blinding for study participants who receive treatment. All pills will be identical in size but there will be two colors of masking encapsulation – blue and bi-colored. This is to help the participant remember to take two different tablets (naproxen/placebo and omeprazole/placebo) at each time and thus reduce the possibility of ingesting two identical pills. The only person who will know which capsules contain active vs placebo will be the unblinded pharmacist responsible for ordering the medication, re-encapsulating the agent, filling the numbered medication vials with the appropriate drug and number of capsules, and handling drug accountability. This person will have no other involvement with study staff or be involved with any study procedures. Unmasking should not be required during the study. If allocation assignment needs to be made available, this will be done based on the circumstances outlined above. If there should be a question regarding proper allocation of treatment product, it would be possible to ascertain placebo from active drug product by opening the treatment capsules and determining if there were an enclosed tablet present. This will be prevented by sealing of all capsules prior to their being placed in treatment vials for dispensing. As mentioned above, the blinded assessor inquiring about medication compliance and adverse events will remain blinded to the treatment arm as the other study staff are, but will not be blinded to treatment versus no-treatment group assignment.

Randomization and drug allocation based on this scheme will be completed by NUCATS and Northwestern's Research Pharmacy, respectively, to ensure blinding. A pharmacist not involved in any other part of the study and without access to study data will be responsible for dispensing

the study medication into bottles and labeling these vials with the PIDs according to the design implemented and drug accountability for both rescue and study agents. The randomization list will be maintained by the pharmacy and be made available to the study PI and study physician only in case of emergency. Un-blinding will only occur if knowledge of the treatment arm would be essential for the safety of the participant. None of the study staff will have access to the randomization list and all study supplies will be identical in appearance other than the PID. All study staff, including the statistician, will remain blinded until database lock. Un-blinding will not take place until the end of the study when the final neuroimaging contrasts will be performed. Preliminary analyses of the data will also be conducted in a blinded fashion using an automated method in which all participants are processed in the same way. An initial platform of analyses including pre-processing, regressors for spontaneous pain episodes, and brain connectivity during resting states can easily be created while remaining blind to the intervention. These preliminary analyses will be first be re-coded and scrambled by someone in the lab who has no other connection to the study, which thus allows other study personnel using this data to remain blinded during preliminary analysis and throughout the study's entirety. Additionally, since there is a no treatment group, measures to continue the partial blind (on the end of the research team) will be done. For the duration of the study, separate personnel (a designated unblinded monitor) will be involved in organizing participant folders, printing questionnaire responses, evaluating interim responses, adverse events, and medication compliance, and walking with participants to collect their medication. This is to ensure that those collecting and analyzing the data can maintain their blind not only to treatment type but also to whether or not treatment was given. Other than the pharmacist and unblinded monitor, the rest of the study staff will remain totally double-blinded and will only be involved in scanning procedures, and sending questionnaires online.

5.5 Visit Windows

Not all participants will be able to come back for their next visit exactly 7 or 21 days from the previous visit. To account for holidays and individuals' personal schedules, the acceptable window for each visit will be ± 5 days from the target date. This window will also be incorporated into pharmacy ordering and pill counts to ensure sufficient amounts of study medication between visits.

6.0 RESPONSE CRITERIA

Treatment response is defined as a reduction in VAS pain intensity $>$ or equal to 20% from visit 1-visit 2 pain ratings, or by permutation testing for change in pain rating by 0.05 p-value. Such individuals are considered treatment "responders," whereas "non-responders" are defined as individuals who experience increased or stable pain levels throughout treatment periods, including reductions in pain $<$ 20% of baseline pain intensity.

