1.3 Predictive neural and behavioral biomarkers for clinical placebo

Summary of main findings from Phase 1 Report:

1. Using the smart phone pain ratings and within subject permutation method provides a robust method for classifying placebo responders and non-responders.
2. Three emotion-related personality outcome measures (MAIA-not worry, MAIA-emotion, ERQ-suppress) together predict future placebo response at 94% accuracy. These measures are also correlated to questionnaires regarding alternative and complementary medicine including MISS (suggestibility), HCAMQ (holistic subscale), and MLHC (health locus of control).
3. Resting state fMRI brain network information sharing between the frontal cortex and somatosensory cortex predicts placebo response at a very high accuracy.
4. Somatosensory cortex grey matter density predicts placebo response.

5. Brain white matter myelination properties do not predict placebo response.
6. Brain grey matter neurite orientation properties do not predict placebo response.
7. Limbic brain right to left asymmetry predicts placebo response.
8. The combined brain and personality final model predicts placebo response at 94% accuracy.

Conclusions from Phase 1 report:

1. The primary conclusion of these results is our ability to demonstrate that clinical placebo response is predictable from personality and from brain properties.
2. Identified personality parameters are distinct from those hypothesized in healthy subjects for experimental manipulations, and are consistent with CBP involving emotional circuitry. The relationship between these and attitudes to alternative medicine suggest common underlying mechanisms.
3. Functional information sharing results are based on a specific hypothesis we derive from our earlier similar study conducted in osteoarthritis patients, suggesting shared mechanisms of clinical placebo response predictive circuits.
4. The cortical gray matter prediction of placebo seems linked to the functional information sharing circuit and probably reflects inter-related measures.
5. The fact that we did not find a whole-brain contrast in white matter myelination properties to predict placebo response was expected and not surprising. It is possible that the white matter connectivity between the functional networks may still be distinct (remains to be tested).

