2.3 Endpoints

- 2.3.1 Endpoint for primary objective: (1) Placebo response (defined as > 20% reduction in pain intensity following placebo treatment, or defined from pain app ratings using permutation with 0.05 p-value cut-off) versus active treatment response (reduction in pain intensity following naproxen/omeprazole treatment)
- 2.3.2 Endpoints for secondary objective: (1) Testing the specificity and sensitivity of the brain and behavioral parameters from Phase 1, in combination with the TOPPP developed from the study interviews, as predictive markers for response in Phase 2. These parameters will be considered validated if together are at least 80% accurate in stratifying responders from non-responders.
- 2.3.3 Endpoint for gender objective: (1) Testing for females showing higher incidence of placebo response using combined outcomes from phase 1 and phase 2 data.

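### Section 6.0's responder and non-responder definitions overlap: a significant fall in pain of less than 20% meets both, and nothing says which label prevails

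*Combined protocol and SAP*

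**What the plan says.** Section 6.0 gives two routes to being a responder. One is a fall of at least 20% from the visit 1-visit 2 ratings. The other is stated as "or by permutation testing for change in pain rating by 0.05 p-value". Non-responders then "are defined as individuals who experience increased or stable pain levels throughout treatment periods, including reductions in pain" of less than 20% of baseline. That clause does not mention the permutation result.

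Section 2.3.1 repeats both routes for placebo response: "defined as > 20% reduction in pain intensity following placebo treatment", "or defined from pain app ratings using permutation with 0.05 p-value cut-off".

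Two other endpoints need the same observed label. Section 2.3.2 says: "These parameters will be considered validated if together are at least 80% accurate in stratifying responders from non-responders". Section 2.3.3 is described as "Testing for females showing higher incidence of placebo response using combined outcomes from phase 1 and phase 2 data".

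The nearest thing to a precedence rule is the Phase 1 summary in section 1.3: "Using the smart phone pain ratings and within subject permutation method provides a robust method for classifying placebo responders and non-responders". Section 8.2 adds that Phase 2 methods will stay close to those of Phase 1, and 8.2.1 carries over the Phase 1 pain measures.

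**The concern.** A two-way classification must give each patient one label. Here a patient with a 12% fall and a permutation p-value below 0.05 is a responder by the second route and a non-responder by the next clause. The 80% rule is a pass/fail criterion, so its reference label should be settled before anyone can see how the model performs under each version. The pooled gender comparison also needs the same label in both phases.

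Three smaller gaps belong to the same edit:
- The permutation route tests for change without a direction, so read literally a significant rise in pain would also qualify.
- The cut is strictly above 20% in 2.3.1 but 20% or more in 6.0.
- Section 6.0 names the baseline ratings but not the treatment ratings compared with them. Objective 2.1.2 speaks of responses seen when treatment ends, which points to late ratings without defining a window.

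**Working it through.** The plan has no figure of its own to reproduce here. The check has a logical part, which needs no assumption, and a numerical part, which does.

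**1. Logic.** Apply the section 6.0 rules to each combination of fall and p-value:

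| Fall | p < 0.05 | p ≥ 0.05 |
|---|---|---|
| under 20% | both labels | non-responder |
| 20% or more | responder | responder |

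Only the top-left cell is contradictory.

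**2. Can that cell be reached?**
- From the plan: two ratings a day (5.2.1), 14 baseline days, 42 treatment days, 75% app compliance (1.2).
- Ratings: 2 × 14 × 0.75 = 21 at baseline and 2 × 42 × 0.75 = 63 on treatment. An assumed final week gives 2 × 7 × 0.75 = 10.5, taken as 10.
- Assumed: within-person SD of 1, 1.5 or 2 points; baseline mean 6; independent ratings.
- Smallest significant fall = 1.96 × SD × √(1/n_b + 1/n_t) / 6.
- 21 v 63 ratings: 8.2%, 12.3% and 16.5%. All are below 20%.
- 21 v 10 ratings: 12.6%, 18.8% and 25.1%. At SD 2 the threshold passes 20%, so little overlap is left.

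**3. How many patients?** From the plan: responders fall by 2.5 units with SD 3 (8.1.2), and half of patients respond (8.1.1). Assumed: person means N(6, 1.3), screened at a baseline mean of at least 5; non-responder change with mean 0 and SD 0.3 to 3; ratings clipped to 0-10; a t-approximation to the two-sided test. There were 40,000 simulated patients per setting, about 31,000 after screening. Share with a significant decrease of less than 20%:

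| Ratings | SD 1 | SD 1.5 | SD 2 |
|---|---|---|---|
| 21 v 63 (six weeks, 75% compliance) | 10-15% | 6-10% | 4-6% |
| 28 v 84 (six weeks, full compliance), all SDs together | 5-17% | | |
| 21 v 10 (assumed final week) | 6-9% | 2-3% | about 1% |

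A true 999-shuffle test at 21 v 63 gave 9.5-14.7%, 6.5-10.2% and 3.5-5.5%.

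Placebo completers = 90 × 140/210 = 60, assuming equal attrition across arms. So 4-15% is about 2 to 9 patients, and 1-9% is about 1 to 5.

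**4. Effect on the 80% rule.** Section 1.3 reports: "The combined brain and personality final model predicts placebo response at 94% accuracy". Take 94% as accuracy on one label, and let d be the share of patients on whom the two labels disagree. Accuracy on the other label is 0.94 − d + 2x, where x (0 to 0.06) is the share both misclassified and discordant. If classifier errors are independent of discordance, x = 0.06d and accuracy is 0.94 − 0.88d. Section 2.3.2 states no denominator; the 60 placebo completers are assumed, so passing means at least 48 of 60 correct.

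| d | Accuracy | P(≥ 48 of 60) |
|---|---|---|
| 4% | 0.905 | 0.996 |
| 10% | 0.852 | 0.902 |
| 15% | 0.808 | 0.637 |

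- Expected accuracy reaches 0.80 at d = 0.14/0.88 = 15.9%.
- In the Phase 2 settings it goes lower only at full compliance with SD 1 and non-responder SD about 0.6-0.9: d = 16.6%, accuracy 0.794.
- With the final-week window the largest overlap, 9%, gives 0.94 − 0.88 × 0.09 = 0.861.
- Without independence, d = 15% gives 0.79 to 0.91.

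**5. The opposite cell.** A fall of at least 20% with p ≥ 0.05 is now clearly a responder. At 21 v 63 this cell is practically empty (under 0.1%). At 21 v 10 it holds about 0.5% of patients at SD 1.5 and 3-4% at SD 2, which at SD 2 is more than the overlap.

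**6. Limit of the model.** Real ratings are probably serially correlated. In a separate permutation check (21 v 63, 400 patients per setting), patients with no true change fell in the overlap about 2% of the time with independent ratings and 6-13% with autocorrelation 0.5.

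**The case against.** The strongest reply is that the plan already signals the answer. Section 1.3 presents within-subject permutation as the Phase 1 classification method, 8.2 carries Phase 1 methods forward, and pooling the phases for gender needs a compatible label. This favours permutation, but by inference only: 2.3.1 keeps both routes, and 6.0 expressly counts falls under 20% as non-response. Nor can the word stable in 6.0 be read as not significantly changed, because falls under 20% are included without condition.

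The second reply is that the size depends on the window, and that objective 2.1.2 points to late ratings, where the overlap is smaller. This stands, and is why both windows are shown.

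The third is that direction is clear in intent, since 6.0 opens with a reduction and counts increased pain as non-response, and that strict versus non-strict 20% rarely matters for averaged ratings. Both are fair; these are tidying points.

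A reader might also infer that the ambiguity runs through the whole trial. The documents do not support that. Equation 1 assigns the strata from baseline predictors, the mixed model in 4.4 uses daily pain, and the pain-change power calculation in 8.1.2 uses mean falls. Section 8.2 describes three codes for responders and non-responders but does not say whether they hold observed or predicted labels, so no effect on the imaging analyses can be asserted.

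**Conclusion.** The contradiction is on the face of section 6.0 and rests on no assumption. It is a stated rule that conflicts with itself, not a missing detail, and it governs three named endpoints.

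Its size is illustrative. With a within-person SD of 1-2 points, about 4-15% of patients are double-labelled over six weeks at 75% compliance (up to about 17% at full compliance) and about 1-9% over an assumed final week. Measured accuracy can move by up to that share.

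A reader might conclude that the choice of label decides whether the model is validated. Under the planned Phase 2 effect it changes the chance of passing but does not generally reverse the expected verdict; one corner of the settings falls just under 80%. Substituting the 25% fall that section 1.2 expects for two weeks of placebo in Phase 1 (assumed between-patient SD 5-15 percentage points) raises the overlap to 9-23%, and expected accuracy could then drop below 80%. That is not the effect on which Phase 2 is planned, so it does not support the stronger claim.

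The sponsor should correct this before unblinding. It does not undermine the design.

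**What to change.** Before unblinding, state one primary label, worded identically in 2.3.1, 2.3.2, 2.3.3 and 6.0, with non-responder as its exact complement. The permutation label is the natural primary, because section 1.3 gives it as the way Phase 1 responders were classified. Possible wording:

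*Responder: the mean app pain rating is lower in the treatment window than in the baseline window, and the within-subject permutation p-value, computed by the Phase 1 procedure, is below 0.05. Non-responder: every other participant with ratings in both windows.*

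With it:
- Delete the clause that counts falls under 20% as non-response.
- Use one form of the 20% cut throughout.
- Name the treatment window, reconciled with objective 2.1.2 and the Phase 1 procedure.
- Report the 20% label as one named sensitivity analysis, with a 2x2 cross-table against the primary label and accuracy under both.

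If the sponsor prefers the 20% label as primary, the same complementary wording and cross-table apply.

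The cost is wording in four places and one extra analysis of data already collected. Downsides to disclose:
- The two accuracy figures may differ.
- A permutation-only label counts some falls under 20% as response, while a 20% label would test the Phase 1 model against a different outcome from the Phase 1 classification.
- With a short window, permutation-only wording can turn patients who are now clear responders (fall of at least 20%, p ≥ 0.05) into non-responders: about 3-4% at SD 2 with one week, essentially none with six weeks.

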7.0 ADVERSE EVENTS AND SAFETY ASSESSMENT

7.1 Adverse Event Collection

7.1.1 We will collect all adverse reactions reported for all treatment groups. We collect all AEs (even colds and coughs or any preexisting condition that may have worsened) regardless if they are related to the study or not. Our IRB guidelines state "any change in clinical condition of the participant obtained upon interaction with the participant during the visit or interval, related or unrelated to the study. Health status will be elicited by asking the participants if there has been any change in their overall health or health status rather than asking specifically regarding predefined conditions (open-ended questioning)".

7.1.2 All AEs will be reported to [name], the study physician, for review and appropriate follow-up.

7.2 Adverse Event Monitoring

Adverse event data collection and reporting, which are required as part of every clinical trial, are done to ensure the safety of subjects enrolled in the studies, as well as those who will enroll in future studies using similar agents. Adverse events are reported in a routine manner at scheduled times during a trial. Additionally, certain adverse events must be reported in an expedited manner to allow for optimal monitoring of patient safety and care.

All patients experiencing an adverse event, regardless of its relationship to study compound/drug, will be monitored until:

- the adverse event resolves or the symptoms or signs that constitute the adverse event return to baseline;
- any abnormal laboratory values have returned to baseline;
- there is a satisfactory explanation other than the study compound/drug for the changes observed; or
- death.

The reporting of adverse events, serious adverse events and unanticipated problems will be done according to the guidelines of the Northwestern University IRB and the FDA*. As of August 20, 2007, Northwestern University IRB requires immediate filing of internal or external adverse events reports, or safety reports only if they have been determined by the Principal Investigator to contain a report of unanticipated problems involving risks to subjects or others. NU considers unanticipated problems, in general, to include any adverse event, incident, experience, or outcome that meets all of the following criteria: (1) Unexpected (in terms of nature, severity, or frequency) given: (a) the research procedures that are described in the protocol-related documents, such as the IRB-approved research protocol and informed consent document; and (b) the characteristics of the subject population being studied. 1. The known or foreseeable risk of adverse events associated with the procedures involved in the research that are described in: a) the protocol-related documents, such as the IRB-approved research protocol, any applicable investigator brochure, and the current IRB-approved informed consent document; and b) other relevant sources of information, such as product labeling and package inserts; or 2. The expected natural progression of any underlying disease, disorder, or condition of the subject(s) experiencing the adverse event and the subject's predisposing risk factor profile for the adverse event. (2) Related or possibly related to participation in the research (in this guidance document, possibly related means there is a reasonable possibility that the incident, experience, or outcome may have been caused by the procedures involved in the research); and (3) Suggests that the research places subjects or others at a different or greater risk of harm (including physical, psychological, economic, or social harm) than was previously known or recognized.

NOTE:

The following events are considered a serious adverse event and would place subjects at a greater risk of harm:

- *results in death;*

- *is life-threatening (places the subject at immediate risk of death from the event as it occurred);*
- *results in inpatient hospitalization or prolongation of existing hospitalization;*
- *results in a persistent or significant disability/incapacity;*
- *results in a congenital anomaly/birth defect; or*
- *based upon appropriate medical judgment, may jeopardize the subject's health and may require medical or surgical intervention to prevent one of the other outcomes listed in this definition (examples of such events include allergic bronchospasm requiring intensive treatment in the emergency room or at home, blood dyscrasias or convulsions that do not result in inpatient hospitalization, or the development of drug dependency or drug abuse).*

Unanticipated problems involving risks to subjects or others should be reported to the IRB within 10 working days (unanticipated deaths of subjects enrolled at NU or Affiliates need to be reported within 24 hours).

All adverse events deemed to be serious, both unexpected and expected, will be reported to the medical monitor.

The medical monitor ([name] [name]) is required to review all unanticipated problems involving risk to volunteers or others, serious adverse events and all volunteer deaths associated with the protocol and provide an unbiased written report of the event to the FDA*. The medical monitor will comment on the outcomes of the event or problem and in the case of a serious adverse event or death comment on the relationship to participation in the study. The medical monitor will also indicate whether he/she concurs with the details of the report provided by the study investigator. Reports for events determined by either the investigator or medical monitor to be possibly or definitely related to participation and reports of events resulting in death will be promptly forwarded to the FDA MedWatch Online Reporting System. Note that since the study is not being conducted under an Investigational New Drug Application (IND), mandatory reporting of safety information to the FDA itself is not required. Instead, voluntary reports of adverse events observed or suspected for human medical products will be filed in the online system specified here.

A summary table of adverse events collected will be submitted at least annually to the Northwestern IRB. Additionally, NCCIH will be informed of serious and non-serious adverse events according to the requirements outlined section 6.2.1 below. **7.2.1. Reporting of SAEs**

SAEs that are unanticipated, serious, and possibly related to the study intervention will be reported to the Independent Monitor, IRB, and NCCIH in accordance with requirements.

- Anticipated or unrelated SAEs will be handled in a less urgent manner but will be reported to the Independent Monitor, IRB, NCCIH, and other oversight organizations in accordance with their requirements.
- Unexpected fatal or life-threatening AEs related to the intervention will be reported to the NCCIH Program Officer within 7 days. Other nonserious and unexpected AEs related to the intervention will be reported to the NCCIH Program Official within 14 days.

